### Background and Significance

The prevalence of dysphagia may be as high as 22% in individuals over 50 years of age (Howden, 2004). There are few therapeutic options and minimal management strategies offered to treat these individuals and improve sequelae of dysphagia.

Dysphagia contributes to malnutrition, aspiration, pneumonia, reduced quality of life and increased mortality in neurodegenerative disease such as ALS (Tabor et al 2016, Chen, 2005; Burkhead, 2014). One reason for this is the lack of normative data across various measures of swallowing and respiratory function. As a result, detecting early impairments in swallowing physiology is difficult, given the variability of swallowing and unknown normative value range of swallowing physiology. Therefore, the goal of this study is to complete clinical tests of swallowing and cough function in healthy volunteers to establish normative data. This will contribute to future study in disordered populations, to determine degree and severity of impairment and efficacious treatment and management strategies based on impairment.

Purpose: The purpose of this study is to establish normative values for clinical testing measures of swallow, respiratory and cough functions. This will aide in establishing degree of impairment in disordered populations, and in identifying efficacious treatment paradigms for dysphagia.

### Study Setting

Swallowing Systems Core Laboratory in Shands Hospital at the University of Florida (DG 130, 136, DG 76 and DG 77).

### Population and Sampling Data

Participants will include up to 120 adults, both males and females across the lifespan. The primary goal of the proposed study is to establish normative data for comparison

with disordered dysphagic populations in an age and gender matched fashion. This study represents a pilot study and the work proposed and comparisons planned have not yet been performed in the dysphagic population using clinical testing measurements. Given that some volunteers may not be able to complete all required tasks and lead to missing data we will recruit and run 20% additional than our target number of 100 for a total of 120 participants. drop and some data may not be included, we plan to study approximately 100 participants. A power analysis is not included in the protocol as we are conducting the first study to collect normative data and establish a database of 'normal' functioning across various swallow and respiratory parameters.

#### Inclusion/Exclusion Criteria.

A total of 120 individuals will be included in this study. Subjects will include both male and females who are aged between 18-100, healthy and with no major medical conditions. Adults who are pregnant, or those with major medical conditions (i.e., swallowing impairment, brain injury) will be excluded from this study. Anyone with allergy to barium will be excluded from this study. No specific gender or race will be excluded or targeted for participation in this study.

#### Recruitment Plan and Consenting Process

Potential participants will be identified through word of mouth, Health Street and advertising via approved flyers within the University of Florida campus and surrounding areas of Gainesville. We will also post approved flyers advertising participation in the study. Interested volunteers will be given an informed consent and given ample time to read over this and ask any questions and given the option to take home informational material to determine if they would like to participate. Prior to consenting, all participants will be screened to determine eligibility for the study. To determine if you are eligible for the study, who are considered to be of childbearing age (less than 60 years) will be asked to complete a pregnancy test to confirm they are not pregnant prior to performing the exam. If a person consents to be in the study, they will sign the ICF document and provided with a hard copy of the consent material. Study personnel will arrange a single, one-hour appointment time to perform the study. No costs will occur for being in this study. Each participant will receive a parking voucher, as needed, for participating in the study and a \$50 compensation will be provided to each volunteer to cover any expenses associated with attendance

#### Protocol:

This study will involve a **single 90-minute visit**. All women under the age of 62 will be asked to complete a pregnancy test as part of the screening process during to radiation

exposure. Eligible participants will then undergo testing to determine their individualized Maximum Expiratory Pressure (MEP), maximum inspiratory pressures (MIP), voluntary and reflexive cough testing, tongue pressure testing and a comprehensive instrumental swallowing evaluation (that will include either videofluoroscopy, manometry, or simultaneous swallowing and manometry study). The entire duration of the exam will be under 90 minutes and the participant will be free to leave at any point during the examination.

Procedures:

Respiratory Testing:

The participants' maximum expiratory/inspiratory pressure (MEP/MIP) will be assessed using a hand-held digital manometer (MP01, Micro Direct Inc.). The subject will be standing and while wearing a nose clip be asked to blow out as hard and fast (MEP) or in as hard as they can (MIP). Forced vital capacity (FVC), a maximum effort breathing test assessing maximum volume exhaled, will also be completed. These tests will be completed a maximum of three times to obtain values within close range of one another. Subjects will also complete maximum effort cough testing, both voluntary and reflexive testing using a spirometry and pneumotachograph setup (Lab Chart Version 7).

Videofluoroscopy and Barium:

The swallowing systems core laboratory is fully equipped to perform videofluoroscopy with a c-arm (OEC 9900) that is dedicated solely to research purposes.

Videofluoroscopy recordings will be kept to a minimum and turned on only during completion of a specific testing task. Video recording and images captured during the videofluoroscopy will be synced and saved for data analysis. Videofluoroscopy allows for time-synced, frame-by-frame data analysis for the specific measures taken during swallowing tasks. The physiological swallowing measures (temporal and kinematic movement of the base of tongue and hyolaryngeal complex during swallowing) to be analyzed cannot be visualized with any other technique. All swallowing tasks will be completed using barium in order to visualize the bolus during movement of various swallowing muscles and structures. A standardized barium protocol will be administered that will include thin liquid, nectar thick liquid, honey thick liquid, pudding and a solid cracker. We do not expect aspiration (bolus into trachea) to occur during this study given we are recruiting individuals with no prior history of disease or disorder, and aspiration is uncommon in normal swallowing individuals. Swallowing tasks during videofluoroscopy will consist of comfortable size cup sips/bites in various head positions (i.e., head turned, chin tucked down). In addition to swallowing trials, the participant may be asked to perform a list of commonly utilized swallowing therapeutic maneuvers

that will include: a chin tuck, a head turn to the left and right, a tongue press maneuver and a breathing maneuver to allow quantification of the physiologic impact of these tasks on the upper aerodigestive tract in healthy adults. These tasks will also be utilized during the High Resolution Manometry procedure, explained below.

#### High Resolution Manometry:

During the manometry portion of the evaluation, we will be using a small pressure tube that gets inserted into the nose and travels down to the back part of the throat. After the tube is in place in the throat, the subject will sit comfortably for five minutes to acclimate to the tube being in this position. After this time, they will be asked to swallow several teaspoon-sizes of a saline solution. Saline is a thin-water like solution that has a slightly salty taste. They may feel a slight discomfort as the tube is being placed in position and as they begin to swallow the saline with the tube in place. Time to complete all swallowing-related tests will be approximately 30 minutes and participation in this study will require only one visit. Individuals have the option to decline this procedure if uncomfortable or difficult to tolerate.

#### Tongue Pressure Examination:

During the tongue examination, we will measure tongue strength and the maximum amount of time that the subject can apply pressure to an air-filled tongue bulb that will rest on the roof of your mouth. Lingual function will be evaluated using the Iowa Oral Pressure Instrument (IOPI). The Iowa Oral Pressure Instrument (IOPI) model 2.3 is a device that measures the peak pressure performance of lingual strength and endurance via the action of a bulb placed on the hard palate. The patient elevates the tongue to touch the roof of the mouth and pushes against the bulb. To assess maximum anterior isometric pressure, the bulb will be placed on the roof of the mouth and the participant will raise his or her tongue to apply pressure to this bulb and then quickly release the tongue back into a neutral position.

#### Tongue Function Testing:

We will also perform a technique called electrical impedance myography (EIM) of the tongue. EIM allows us to learn more about the health of the composition of the tongue muscle. We will gently rest a small tongue depressor containing a special sensing electrodes on the top of the tongue. We will then have the subject close their mouth for two seconds while the electrode obtains information about the composition of your tongue. They will not feel anything while the tongue depressor is resting on your tongue.

#### Cough

*Voluntary Cough Testing:*

Voluntary cough function will be assessed using an oral pneumotachograph (MLT 1000, ADInstruments, Inc; Colorado Springs, CO), connected to a spirometer filter (MQ 304 Spirometer Filter, Vacumed; Ventura, CA) during voluntary cough production. The participant will be seated with a respiratory facemask held in place by the examiner and instructed to complete three tidal breaths into the facemask, take a deep breath in and then “cough hard like you have something stuck in your throat”. This task will be modeled to the patient by the examiner and practiced first to ensure the patient understands the procedure. Airflow signal will be measured, low pass filtered at 150Hz, digitized at 1 KHz and displayed on a portable laptop computer using Chart Version 7 (Microsoft Corp; Redmond, WA).

*Reflexive Cough Testing:*

Participants will be outfitted with a facemask covering the nose and mouth. The facemask will be coupled to a pneumotachograph, differential pressure transducer, and have a side port with a one-way inspiratory valve for nebulizer connection. The nebulizer will be a DeVilbuss T-piece connected to a dosimeter that delivers aerosolized solution during inspiration with a delivery duration of 2 seconds. The cough airflow signal will be digitized (Power Lab Data Acquisition System) and recorded (LabChart 7; ADInstruments, Inc) to a computer for offline analysis. Participants will be seated for an initial 30 seconds of quiet breathing in order to acclimate to the facemask. Participants will then complete a capsaicin challenge with three randomized blocks of 0, 50, 100, 200, and 500  $\mu$ M capsaicin. The capsaicin will be dissolved in a vehicle solution consisting of 80% physiological saline, and 20% ethanol. Participants will be given the instruction “cough if you need to” prior to capsaicin delivery. The solution will be administered automatically upon detection of an inspired breath and there will be a minimum of one minute between each trial. After each inhalation of the capsaicin solution, participants will be asked to rate their urge-to-cough (UtC) on a modified Borg scale, ranging from 0 (no urge to cough) to 10 (maximal urge to cough). Participants will be provided water to drink between trials. Members of our research team have extensive experience using this methodology for the induction of reflex cough (Hegland et al., 2012; Wheeler-Hegland et al., 2014), and we have a FDA IND # 76866 for the use of capsaicin in the study of cough reflex sensitivity and motor pattern.

Data Collection Procedures

The principal investigator will be responsible for safety and monitoring data (oversight plan). The data will be collected and recorded by the principal investigator and her research assistants who will enter data into the research database. Data will be kept in

a locked cabinet within a locked laboratory. All data entered into the database will be coded to remove participant identifiers and this database is backed up daily. Data accuracy will be verified by double data entry. That is, following initial data entry the research assistant and /or principal investigator will verify the data entered into the database. Data verification will take place prior to any analysis of these data. Data, adverse events and individuals subject safety will be routinely monitored throughout each subject evaluation by the PI. A regulatory binder will be kept, in accordance with the IRB-01 Researcher Tools. Any adverse event will be immediately reported to the IRB (using Regulatory Serious and Adverse Unexpected Event Form). Early closure of the study may occur if the team is unable to enroll subjects, or subsequent to unexpected adverse events. However, neither of the events are anticipated.

### Risks/Benefits Analysis

- This research study involves exposure to radiation from x-rays. The radiation exposure you will receive from the swallowing test (videofluoroscopy) is about 50 millirem. This radiation exposure is equivalent to 60 days of natural background radiation to which people in the United States receive each year. The risk from this radiation exposure is considered to be minor when compared with other everyday risks. However, the effects of radiation add up over your lifetime. Repeated exposures may increase your risk of injury or disease. When deciding to enter this study you should consider previous and future potential exposures. Examples would include x-rays taken for a broken bone or radiation therapy treatments for cancer. The investigator will provide you with a contact person if you would like more information about radiation exposure.
- The risk from this radiation exposure is considered to be minor when compared with other everyday risks. However, the effects of radiation add up over your lifetime. Repeated exposures may increase your risk of injury or disease. When deciding to enter this study you should consider previous and future potential exposures. Examples would include x-rays taken for a broken bone or radiation therapy treatments for cancer. The investigator will provide you with a contact person if you would like more information about radiation exposure.
- Barium will be the material used to help us see your swallow function and sometimes when testing is done the barium may enter your lungs during swallowing causing you to cough or feel some discomfort. While small amounts of barium ingested into the lungs does not pose a significant health risk, large amounts ingested over several days can lead to aspiration pneumonia, which is a bad respiratory infection. Therefore, we will stop the test if we see barium enter the airway on more than two swallows of liquid or food to prevent major health risk.
- The 'hot pepper' vapor we will use to make you cough during this part of the testing contains capsaicin, which comes from hot peppers. It may cause a hot sensation in your mouth and throat. This will go away within a few seconds after you stop inhaling breathing the capsaicin vapor. Water will be available to you whenever you want it.

- Although not common, it is possible that you will experience jaw and throat muscle soreness after you are done completing the tongue strength and endurance trials. This discomfort should be temporary and subside within 48 hours.

### Outcome Measures:

This study has several outcome measures because the goal is to establish normative parameters for a variety of clinical tests. The outcome measures include: maximum expiratory/inspiratory pressures (MEP/MIP), which will be assessed using a hand held digital manometer (Micro Mouth Pressure Meter, MP01, Micro Direct Inc.). In order to measure MEP, the participant will be seated with the nose occluded with a nose clip. After inhaling to total lung capacity, the participant will place his or her lips around a disposable mouthpiece and blow out as forcefully as possible. Numbers are then recorded with the maximum across all three trials used for data analysis purposes.

Additional outcome measures include maximum effort results from: high resolution manometry (pressure recordings), swallowing timing and kinematics (swallow study) and tongue pressure recordings (tongue testing). The procedures of these tests are described above.

### Data Analysis

Data analysis will be primarily descriptive, including central tendency, range and standard deviation in order to determine average values for each of the completed tests. This will help to create the database for normative parameters for swallowing and respiratory tasks.

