### Implications

This study will provide researchers and clinicians with the data to compare disordered populations with normative parameters across clinical testing procedures. The results will contribute to evidence for identifying disorder and subsequently recommending certain swallowing therapy approaches.

None of the study members on this team have a financial interest or conflict of interest.

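### The plan sets no limit of normal and no target false-positive rate, and central tendency, range and SD do not supply one that is chosen or constant across tests

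*Protocol*

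**What the plan says.** The protocol's Data Analysis section is two sentences long. The first reads: "Data analysis will be primarily descriptive, including central tendency, range and standard deviation in order to determine average values". The second says that this will help build the normative database. The section names no percentile, reference limit, confidence interval, distribution check or transformation.

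The intended use is wider than averages:

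- Background and Significance gives as a reason for the study that early impairment is hard to detect, "given the variability of swallowing and unknown normative value range of swallowing physiology". Of the norms it says: "This will aide in establishing degree of impairment in disordered populations".
- Population and Sampling Data plans comparison with "disordered dysphagic populations in an age and gender matched fashion".
- Implications adds: "The results will contribute to evidence for identifying disorder and subsequently recommending certain swallowing therapy approaches".

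On numbers, the protocol says "we will recruit and run 20% additional than our target number of 100 for a total of 120 participants" and "A power analysis is not included in the protocol". Eligible adults are "aged between 18-100, healthy and with no major medical conditions", with no age or sex quotas.

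The SAP does not fill the gap. Experiment #1 plans comparisons of people with ALS against matched healthy controls, and Experiment #2 a mixed model for laryngeal vestibule closure timing. SAP Table 1 labels the cough thresholds and urge-to-cough ratings ordinal.

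**The concern.** Calling a patient's value impaired requires a limit with a chosen share of healthy people beyond it. The plan will publish a centre, a range and an SD and leave the limit undefined. The limit would then be picked after the data are seen, or improvised by each reader from the published summaries.

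The two obvious improvisations behave badly in different ways. The range widens as more people are tested, so its false-positive rate depends on how many completed that test. Mean ± k SD gives the nominal rate only when the outcome is close to normal. The same label of abnormal could then carry a different specificity from one test to the next, in a study whose product is the norms.

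**Working it through.** **The plan's own figure.** 100 × 1.20 = 120, which matches the stated recruitment. No false-positive rate or reference limit is stated, so there is none to reproduce.

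**Range as the limit.** For a continuous outcome, the share of healthy people below the minimum of n healthy people follows Beta(1, n), with mean 1/(n+1), whatever the distribution.

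| n | Source of n | Expected share below minimum | 95% interval for one realised minimum |
|---|---|---|---|
| 100 | protocol target | 1/101 = 1.0% | 0.03% to 3.6% |
| 50 | assumed | 1/51 = 2.0% | 0.05% to 7.1% |
| 20 | assumed | 1/21 = 4.8% | 0.1% to 16.8% |
| 10 | assumed: 100 spread evenly over 5 age bands × 2 sexes | 1/11 = 9.1% | 0.3% to 30.8% |

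The number tested can differ by test. The Protocol section allows videofluoroscopy, manometry or both; High Resolution Manometry lets participants decline; Population and Sampling Data expects missing data. No count per test is given.

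**Mean ± k SD as the limit.** For a normal outcome with known mean and SD, mean − 1.645 SD flags 5%. With both estimated at n=100, the expected rate is 5.25% (95% interval 2.6% to 9.0%), which is usable.

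For a lognormal outcome (assumption; the documents give no distributions), let σ² = ln(1 + CV²). The share below mean − 1.645 SD is Φ(z), with z = [ln(1 − 1.645 CV) + σ²/2]/σ. The share above mean + 1.645 SD uses the plus sign and 1 − Φ(z).

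- CV 30%: σ = 0.294. Lower z = (ln 0.5065 + 0.043)/0.294 = −2.17, so 1.5% below. Upper z = 1.51, so 6.5% above.
- CV 50%: σ = 0.472. Lower z = (ln 0.1775 + 0.112)/0.472 = −3.42, so 0.03% below. Upper z = 1.51, so 6.6% above.
- CV 100%: 1 − 1.645 is negative, so 0% below. Upper z = 1.58, so 5.7% above.

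**Ordinal outcomes.** Take five levels scored 0 to 4 with three assumed sets of proportions. Mean + 1.645 SD flags 0% for (0, .10, .25, .35, .30), 10% for (.60, .20, .10, .06, .04) and 15% for (.05, .30, .30, .20, .15), against a nominal 5%.

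**What a percentile would give.** At n=100, the 5th ordered value as the limit has an expected false-positive rate of 5/101 = 4.95% (95% interval 1.6% to 9.9%). The distribution-free 95% CI for the 5th percentile runs from the 1st to the 11th ordered value (actual coverage 98.3%). A two-sided, equal-tailed interval of this kind needs 0.95^n ≤ 2.5%, so n ≥ 72: 0.95^72 = 2.49%, while 0.95^50 = 7.7% and 0.95^20 = 35.8%. For the 2.5th percentile none exists at n=100, because 0.975^100 = 8.0%.

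**The case against.** A reader might infer that the plan adopts the range, or mean ± k SD, as its cut-off. It does not: no section makes either one a rule for abnormality. The analysis is described as primarily descriptive and the list is introduced as what it includes, so percentiles are not excluded and could be computed later from the stored data. Central tendency can cover the median. The protocol calls the study a pilot, and degree of impairment can also be expressed as distance from the mean in SD units. All of this stands, and it makes the fault one of omission.

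A reader might also infer that the false-positive rate is unknowable. It is not: the expected rate beyond a sample minimum is 1/(n+1) for any n. What is missing is a chosen rate held constant across tests and age/sex groups.

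The SD argument has limits too. It does not apply to near-normal outcomes. Under the assumed skew, the upper side is off by at most 1.6 percentage points, so the harm depends on which tail marks impairment, and the documents do not say. The ordinal point concerns cough thresholds and urge-to-cough ratings only, and the SAP already compares the thresholds by a rank test.

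Percentiles are not a complete answer either. Ties stop a few-level ordinal outcome from reaching 5%, small n gives no two-sided exact interval, and one pooled percentile can be right overall yet wrong at a given age. The fix has to deal with each of these.

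**Conclusion.** The point holds as an omission that affects what the study can deliver. The norms are meant to establish degree of impairment and help identify disorder, yet neither document sets a limit of normal or a target false-positive rate.

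If the range is used by default, the expected rate below the minimum is 1.0% at the target n and rises to 4.8% at an assumed n of 20. If mean − 1.645 SD is used, the rate is about 5% for near-normal outcomes but 1.5% to 0% under assumed lognormal skew with CV from 30% to 100%; the upper side gives 5.7% to 6.6%. Skewness, the smaller n and the ordinal proportions are assumptions. The ordinal scaling comes from the SAP, and the scope for n to differ by test comes from the protocol.

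The documents do not support saying that the norms cannot grade impairment at all, since better limits remain computable from the same data. The change should be made, preferably before the norms are derived; it does not call the data collection into question.

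**What to change.** Amend the protocol's Data Analysis section as follows:

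- **Continuous outcomes:** make the 5th and/or 95th percentile with a 95% CI the normative statistic, and report the n for each test. State which tail counts as abnormal.
- **Age and sex:** estimate the limit as a function of both, for example by quantile regression or a regression-based limit after transformation, rather than only pooled.
- **Intervals:** for pooled or within-group percentiles, use order-statistic CIs where n is at least 72. Where n is smaller, use a model-based limit after a distribution check or transformation.
- **Ordinal outcomes:** report category proportions.
- **Mean, SD and range:** keep these as description, and state that the range is not the limit of normal.

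The cost is about a paragraph of text and a little more analysis, with no extra participants or procedures. The drawback is that the CIs will show how imprecise the limits are, especially at small n. Users of the norms need to see that.

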Title: Establishing Normal Swallowing and Breathing Profiles in Healthy adults across the age span

NCT: 03122145

Date: March 1, 2019

Experiment #1: Statistical Analysis Plan

Table 1. Test domains and corresponding outcome variables.

Domain	Test	Outcome Variable
Cough	Reflexive cough testing: Capsaicin: (0,50,100,150,200uM) Suprathresholds: Capsaicin: 200uM	-Motor threshold: cough total (ordinal) -Sensory threshold: Urge-to-cough rating (ordinal) -Log transformed Urge-to-cough sensitivity slopes (continuous) -Motor: peak expiratory cough flow (continuous)

Table 2. Specific aims, associated measurements and apriori statistical analyses

Aim		Design	Measurement	Apriori Analysis
1	Reflex cough thresholds	Between group comparison	Sensory and Motor Reflex cough thresholds (ordinal)	Mann-Whitney U test comparing reflex cough thresholds of ALS individuals vs. age/gender matched healthy controls
2	Dose-dependent response curves	Between group comparison	Urge to cough sensitivity (continuous)	A slope calculated by plotting the UTC ratings against capsaicin concentration on a log-log scale, and fitting a linear regression line to the data. Comparisons between ALS vs. controls
3	Voluntary cough	Between group	Peak expiratory cough flow	Mann Whitney U between groups comparison for voluntary cough parameters between healthy controls and individuals with ALS outcomes: peak expiratory cough flow

Experiment #2: Statistical Analysis Plan

For Laryngeal Vestibule Closure (LVC) timing measures, a linear mixed effects model was used to compare the duration of LVC and duration to LVC among the swallow conditions. Pairwise comparisons were used when fixed effects were significant (Sidak corrected). Outcomes from both analyses were significant at $p \leq .05$. Interrater reliability (20% of the data) and intrarater reliability (5% of the data) for the timing of LVC measures were analyzed using single-measure intraclass correlation coefficients (ICCs). ICC estimates and their 95% confidence intervals were calculated with a consistency of agreement definition. All samples were randomly selected for reliability.

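### The primary goal is norms for age- and gender-matched comparison, but the only normative analysis planned gives an average, a range and an SD per test, with no age- or sex-specific value or limit

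*Protocol*

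**What the plan says.** **Goal.** Protocol, Population and Sampling Data, states the primary goal as normative data for comparison "with disordered dysphagic populations in an age and gender matched fashion". Background and Significance explains why: "detecting early impairments in swallowing physiology is difficult, given the variability of swallowing and unknown normative value range of swallowing physiology". Of the resulting norms it says: "This will aide in establishing degree of impairment in disordered populations". The SAP is titled "Establishing Normal Swallowing and Breathing Profiles in Healthy adults across the age span". The Inclusion/Exclusion Criteria admit both sexes from 18 to 100 years, with no age or sex targets.

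**Analysis.** Protocol, Data Analysis, is two sentences long. The analysis is "primarily descriptive, including central tendency, range and standard deviation in order to determine average values for each of the completed tests", and the results feed the normative database.

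**SAP.** Age and gender enter the SAP's analyses once, in Experiment #1, Table 2, Aim 1: "Mann-Whitney U test comparing reflex cough thresholds of ALS individuals vs. age/gender matched healthy controls". In Experiment #2, "a linear mixed effects model was used to compare the duration of LVC and duration to LVC among the swallow conditions". Mouth pressures, tongue pressure and manometry pressures, all listed under the protocol's Outcome Measures, appear in no SAP analysis. The Data Analysis section is therefore their whole plan.

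**The concern.** A single mean and SD over ages 18 to 100 and both sexes describes the mix of people who happened to enrol. It does not say what is normal for a person of a given age and sex, which is what a matched comparison needs. The same applies to the range: its ends are the two most extreme participants, and it tends to widen as the sample grows.

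At stake is the use the protocol gives for the data, namely judging early impairment and its degree. If the summaries are pooled, and a test declines with age or differs by sex, healthy older people of the lower-scoring sex are flagged too often, and real impairment in younger people of the higher-scoring sex is missed. Where a test varies with neither, pooling does no harm.

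**Working it through.** **The plan's own figure.** Target 100 plus 20%: 100 × 1.20 = 120, which matches the protocol. No precision target, SD, effect size or cut-off is stated, so there is nothing else to reproduce.

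**Goal against analysis.** The goal needs values indexed by age and sex. Data Analysis specifies values indexed by test only. SAP Aim 1 uses matching to select controls for a hypothesis test and yields no norm. Experiment #2 contrasts swallow conditions and states no age or sex term. No passage closes the gap.

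**Size of the error if pooled (illustration).** Assumptions, none from the documents: within-cell SD 1; normal residuals; ages uniform on 20–90 (mean 55, SD 70/√12 = 20.2); equal numbers of each sex; women and older people scoring lower; limit = mean − 1.645 SD, intended to flag 5%.

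With age correlation r and sex gap d:
- pooled variance = 1 + r²/(1 − r²) + d²/4
- flag rate = Φ(pooled limit − cell mean)

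For r = 0.3 and d = 1:
- pooled variance = 1 + 0.0989 + 0.25 = 1.349, so SD = 1.161
- limit = −1.645 × 1.161 = −1.911
- woman aged 75: cell mean = −0.5 − √0.0989 × (20/20.2) = −0.811; flag rate = Φ(−1.911 + 0.811) = Φ(−1.10) = **13.6%**
- man aged 25: cell mean = 0.5 + √0.0989 × (30/20.2) = 0.967; flag rate = Φ(−1.911 − 0.967) = Φ(−2.88) = **0.2%**

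Other cases:
- age effect only, r = 0.2 to 0.5: 7–9% at age 75
- sex effect only, d = 0.5 to 1.5: 7–10% of women
- neither: 5%

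**Sampling error.** Simulation with r = 0.3 and d = 1, 20,000 samples per row; regression on age, age squared and sex; flag rate for a healthy 75-year-old woman (mean, and the interval holding 95% of samples). The last column is the 95% CI half-width of the regression limit in within-cell SDs. The n = 60 rows stand for tests with fewer participants; that number is also an assumption.

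| Ages | n | Pooled limit | Regression limit | Half-width |
|---|---|---|---|---|
| Even, 20–90 | 100 | 13.8% (7.6–21.8) | 5.4% (2.0–10.9) | ±0.41 |
| Even, 20–90 | 60 | 14.0% (6.3–24.3) | 5.7% (1.5–13.1) | ±0.52 |
| 70% aged 20–40, 30% aged 40–90 | 100 | 19.7% (11.7–29.2) | 5.6% (1.6–13.0) | ±0.51 |
| 70% aged 20–40, 30% aged 40–90 | 60 | 19.9% (9.8–32.7) | 6.0% (1.1–16.3) | ±0.65 |

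The young-heavy split is assumed. It reflects the warning under Limitations that university recruitment may restrict the age range.

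**Pooled half-width with no effects.** 1.96 × √(1/n + 1.645²/(2n)) = 0.30 at n = 100 and 0.39 at n = 60. With both effects, simulation gives 0.32 and 0.42.

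**Skewed residuals (n = 100, even ages).** Limits from the residual SD flag 0.0% with right-skewed (exponential) residuals and 7.6% with left-skewed ones. Empirical residual percentiles flag 5.1% (0–22) and 5.3% (1.7–11). For a lognormal outcome (log SD 0.3), the residual-SD limit flags 0.1% untransformed and 5.4% (2.0–10.8) after a log transformation.

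**The case against.** Five points can be made for the plan.

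- **The wording is open.** The analysis is described as mainly descriptive with a non-exhaustive list, so summaries by sex and age band would comply. This stands: pooling is not stated, and the harm is conditional on it. But allowing such summaries is not planning them.
- **Matching needs only individual records.** The database could supply matched healthy controls, as SAP Aim 1 does. This also stands, for comparing groups. It does not supply normative values for judging a person, which is the declared purpose.
- **It is a pilot and sets no cut-off.** True, and the 5% limit used here is an assumption. A pilot can do without a power calculation; it still needs an analysis that answers its goal.
- **The size depends on chosen inputs.** The largest figures need two effects together, or a young-heavy sample, and normal residuals. With right-skewed residuals, n = 100 and even ages, the pooled limit flags about 2.7% of the same women, so the error can run the other way. That is still not 5%, but the percentages are illustrations and not estimates.
- **Regression has limits.** It cannot replace older people who were not recruited. The fallback for stubborn right skew is imprecise: 0–22% with even ages and roughly 0–38% with a young-heavy sample. This stands, and is why the fix asks for the supported age range to be stated.

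**Conclusion.** The point holds. The stated primary goal and the only normative analysis do not meet, and the SAP does not bridge them. The data remain usable, so this is a change the sponsor should make and not a fatal flaw.

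The size is conditional. It is nil for a test unrelated to age and sex, roughly 7–10% flagged instead of 5% in the lower-scoring group with one moderate effect, and about 14–20% in healthy 75-year-old women with both effects at r = 0.3 and d = 1. These rest on assumed effects, normal residuals, pooled summaries and a lower 5% limit. That the age- and sex-specific norm is unspecified rests on none of them.

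**What to change.** Amend Protocol, Data Analysis, and add a normative section to the SAP.

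1. **Continuous outcomes** (mouth pressures, tongue pressure, manometry pressures, swallow timing and kinematics, peak cough flow, urge-to-cough slope): regress on age and sex, with a curved age term if needed. Check residuals for skewness and non-constant variance, and transform where needed. Report age- and sex-specific means and 5th and 95th percentile limits with 95% CIs. Use mean ± 1.645 residual SD only if the residuals pass the check; if skew persists after transformation, use the empirical 5th and 95th percentiles of the residuals.
2. **Ordinal outcomes** (cough total, urge-to-cough rating): report medians and frequency distributions by sex and broad age band, with no SD-based limits.
3. Keep the pooled summaries as background. Do not use the observed range as a limit of normal. State for each test the age range over which the limits are supported.

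**Cost.** Some extra analysis and wider intervals. At age 75 and n = 100, the lower limit carries ±0.41 SD with even ages or ±0.51 SD with a young-heavy sample, against ±0.30 to ±0.32 SD for a pooled limit. Empirical residual percentiles cost more, ±0.50 SD even with normal residuals. For comparison, separate limits in three age bands by two sexes (about 17 per cell) would carry about ±0.75 SD, which is why regression is preferred. For ordinal outcomes, two age bands by two sexes leave about 25 per cell at n = 100, so a category seen in half of a cell has a 95% CI of about 32–68% (27–73% with 15 per cell at n = 60). Manometry may be declined, and the swallow examination may be videofluoroscopy or manometry, so those tests will have fewer participants and wider limits. The change can be made within the planned 120. If recruitment is still open, targets by age and sex would help most at the older end.
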